C.2. Study Overview. *Suubi4Stigma*, a mixed-methods sequential explanatory study,⁹³ will address the urgent need for theoretically and empirically informed interventions that seek to reduce HIV/AIDS-associated stigma and its negative impact on child health and psychosocial well-being. We will test the feasibility, acceptability and preliminary effects of the G-CBT versus MFG intervention, two evidence-based interventions that have, to date, been extensively used to address mental health functioning among children and adolescents. Specifically, clinics will be randomized to one of three study arms (see C.3). The conceptual model (Fig 1) specifies the expected relationship between the intervention arms, mechanisms and potential outcomes.

Figure 2. *Suubi4Stigma* Assessment

usual (n=3 clinics; 30 child-caregiver dyads); 2) G-CBT intervention + usual care (n=3 clinics; 30 child-caregiver dyads); and 3) MFG intervention + usual care (n=3 clinics; 30 child-caregiver dyads). Both treatment and control arms will be delivered over a 3-month period. Data will be collected at baseline (pre-intervention), 3-months and 6-months post-intervention initiation. Children in the same clinic will be assigned to the same study condition to avoid contamination (Fig.2).

C.3.1 Study Inclusion/Exclusion Criteria: *Inclusion criteria for children:* The target population for this study is CLWH enrolled in care at a health clinic that has partnered with ICHAD ([name] et al.; *Suubi+Adherence* study). Child inclusion criteria are: 1) HIV+ status- defined as a child tested with confirmation by medical report and has been disclosed to; 2) prescribed ART; 3) living within a family (defined broadly - not necessarily with biological parents); and 4) ages 10 to 14. All eligible CLWH from a particular household will be enrolled in the study and will be assigned to the same study condition. *Inclusion criteria for parents/caregiving families.* Caregivers of CLWH who agree to participate in the study. *Exclusion criteria* includes a significant cognitive impairment of the child or parent that interferes with understanding the informed consent process. *Inclusion criteria for clinics.* Clinics registered and supported by the government to provide ART to CLWH in Masaka.

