C.3.2. Research Setting: The child-caregiver dyads will be selected from 9 health clinics in the Masaka region where Reach the Youth-Uganda (RTY), our collaborating institution, collaborates with over 40 health clinics (see letters of support). Nine clinics will be randomly selected based on size (total number of CLWH served) and location (rural, semi-urban, urban).

C.3.3. Recruitment of Participants: *Screening and Recruitment.* Procedures tested in our previous studies (see C.1.) will be used. Participants will be identified and recruited from the healthcare clinics associated with RTY and ICHAD. A list of all eligible families will be created from medical records. Providers will present the project to adult caregivers of eligible children during appointments. If caregivers are interested, verbal consent to be contacted by research staff (on-site during clinics) will be requested (see human subjects sections).

Informed Consent. During the face-to-face meeting, the child's primary caregiver will read and sign a standard consent form. In doing so, the caregiver will be consenting to participation for themselves and their child. Children will sign an assent form that will be read aloud verbatim. If either the child or the caregiver refuses to participate, they will not be enrolled. (see human subjects section). *Enrollment.* Dyads will be enrolled in one of the three study arms. Only children and their caregivers who meet inclusion criteria will be selected (See C.3.1.). For each of the 9 clinics, a list of "eligible participants" will be generated and used to randomly select 10 children (and their caregivers), constituting the "actual" participants for that clinic. For the qualitative component, dyads with the highest, medium, and lowest levels of attendance in two treatment arms (6 clinics) will be identified post intervention. Two families within each of these groups in the 6 treatment clinics will be invited to participate in qualitative interviews (2x3x6=36 dyads). This sampling method will ensure that participants with varying experiences are represented. This will allow us to identify common patterns and

variations in participants' experiences. The sample size will be sufficient for theoretical saturation,⁹³⁻⁹⁶ and will allow for identification of common patterns and/or variations across participant experiences.

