b) *Acceptability.* We will adapt satisfaction surveys, (e.g., the Client Satisfaction Questionnaire (CSQ-8)) to assess acceptability.¹⁶⁰ Items include: "How satisfied were you with the program?", "How helpful was the program in addressing HIV-associated stigma?" and "How likely are you to recommend this program to other families with CLHA?" Given the modest sample size, quantitative analyses of intervention data will be largely descriptive and concentrate on tabulating and summarizing satisfaction outcomes. In regards to hypotheses and methods for primary preliminary/exploratory analyses *to assess study feasibility*, we expect that: **H1:** Following intervention, relative to the control group, participants in both treatment arms (G-CBT and MFG) will have: **H1a:** lower mean count of children reporting HIV/AIDS-associated stigma; **H1b:** lower mean levels of reported HIV/AIDS-associated stigma and improved child psychosocial functioning; **H1c:** lower mean levels of reported child mental health challenges; **H1d:** higher mean levels of adherence. **H2:** Following intervention, relative to the CBT intervention arm, participants in the MFG intervention will have: **H2a:** lower mean count of children reporting HIV/AIDS-associated stigma; **H2b:** lower mean levels of reported HIV/AIDS-associated stigma and improved child psychosocial functioning; **H2c:** lower mean levels of reported child mental health challenges; **H2d:** higher mean levels of adherence. Children will be the unit of analysis for these primary preliminary analyses. We will plot means by group over time to describe overall patterns of change. We will use linear mixed models (LMMs) to evaluate the proposed hypotheses. We will fit LMMs to ensure that all requisite information is available to perform the types of analyses typically undertaken in a formal RCT of intervention efficacy and to obtain valuable effect size information. LMMs will include random intercepts for clinic membership and random intercepts and slopes for subjects (three-level models). Due to the modest sample size, significance testing will be de-emphasized. Similarly, although the modest sample size precludes formal investigation of moderation, we will use the same LMM approach described above to compare children across study arms over time on the moderators listed in Table 1. Additional analyses will consider the role of child gender as a moderator in line with NIH guidelines addressing the importance of sex and gender as critical moderators. These moderation analyses will be secondary exploratory analyses. Additional exploratory analyses will study parents and children jointly as the unit of analysis via dyadic analysis methods such as actor-partner and means-and-deviation models to quantify parent vs. child stigma effects and between- vs. within-dyad effects on mental health outcomes.^{161,162}

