
Power Analyses. Although the study purpose is to determine preliminary feasibility and acceptability, rather than conduct formal hypothesis tests, we conducted several power analyses using NCSS PASS to supply additional information. Our power analyses assume $\alpha=.05$, power=.80, 81 participants retained at the final time point following 10% estimated attrition, and a clinic-based conservative unconditional ICC of 9.3% based on our previous SUUBI study of mental health in Uganda children.¹⁶³ For the target enrollment proportion of 70% to assess feasibility, the width to the limit of the confidence interval is 27.9% (standardized distance: .32). For continuous standard normal variables to assess acceptability (e.g., CSQ-8), the distance from the mean to the confidence limit is .30. These distances to confidence limits are between small (.20) and medium (.50) effect sizes. For preliminary efficacy exploratory analyses with two time points and paired comparisons of two out of the three groups at 81/3=27 participants per group (N=54 per comparison), minimum detectable standardized mean differences for continuous outcomes ranged from .79 to .97 for within-subjects correlations r ranging from .20 to .80. In sum, our study is powered to detect small-medium distances to confidence limits for descriptive statistics and large longitudinal analysis effects, though hypothesis testing is not the study focus.

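### The detectable differences of .79 to .97 apply a one-visit design effect to a two-visit mean, which shrinks clinic variance that the planned model holds constant; the effect is material mainly at low within-subject correlation

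*Combined protocol and SAP*

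**What the plan says.** The Power Analyses paragraph of C.3.6 Data Analysis sets out its inputs: "Our power analyses assume $\alpha=.05$, power=.80, 81 participants retained at the final time point following 10% estimated attrition". For clustering, the value adopted there is "a clinic-based conservative unconditional ICC of 9.3% based on our previous SUUBI study of mental health in Uganda children". The comparison of arms is described as one "with two time points and paired comparisons of two out of the three groups at 81/3=27 participants per group (N=54 per comparison". The result is that "minimum detectable standardized mean differences for continuous outcomes ranged from .79 to .97 for within-subjects correlations r ranging from .20 to .80". The software is named, but the formula, design effect, contrast and reference distribution are not given.

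The analysis model is in the Aim 1 part of the same section: "LMMs will include random intercepts for clinic membership and random intercepts and slopes for subjects (three-level models". It includes no clinic-by-time term.

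The Study Overview gives the cluster structure, for example "G-CBT intervention + usual care (n=3 clinics; 30 child-caregiver dyads". Under Recruitment of Participants, each clinic's list of eligible children is "used to randomly select 10 children (and their caregivers". With 27 retained per arm, that leaves 27/3 = 9 per clinic.

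**The concern.** Two adjustments have to be combined here: one for repeated measures on the same child, one for children clustered in clinics. Multiplying them is valid only if clinic effects fade between visits at the same rate as individual scores, that is, if a clinic's effects at the two visits correlate only r. The planned model says otherwise, because its single clinic intercept applies at every visit. Averaging two visits reduces occasion-to-occasion noise but leaves the clinic component untouched.

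If the factors were simply multiplied, the stated 80% power does not follow from the plan's own ICC, sample size and model. The apparent gain from a low within-subject correlation is then partly an artefact, and the most favourable end of the range is the most overstated. The plan says that the pilot should supply what a formal efficacy trial would need, so the same formula could be carried forward and understate clustering there.

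**Working it through.** **Inputs.** From Power Analyses: alpha .05 (taken as two-sided), power .80, 27 per arm, two time points, ICC .093, r from .20 to .80. From the Study Overview: 3 clinics per arm, hence 9 retained children per clinic. From Aim 1: a clinic intercept constant over visits. Outcome variance at one visit is set to 1 and taken as equal at both visits.

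**Step 1: which design effect was used.** The one-visit design effect is 1 + (9−1)(.093) = 1.744. Two other figures in the same paragraph test it. The effective total sample is 81/1.744 = 46.4, or 46 rounded down.
- Exact 95% interval for 70% with n = 46: .547 to .826, width .279. The plan prints 27.9%.
- Distance from mean to limit for a standard normal variable: 2.014/√46 = .297. The plan prints .30.

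Both agree, so the 1.744 design effect was in use.

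**Step 2: reproduce the printed range.** Effective n per arm is 27/1.744 = 15.48, or 15 rounded down. The variance of a two-visit mean is (1+r)/2. The detectable difference is (1.960+.842) × √[2 × ((1+r)/2)/15].
- r = .20: 2.802 × √(2 × .60/15) = 2.802 × .2828 = .792
- r = .80: 2.802 × √(2 × .90/15) = 2.802 × .3464 = .970

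Unrounded effective n with a t reference on 52 df gives .795 and .973. The printed ratio .79/.97 = .814 also matches √(.60/.90) = .816. Other contrasts at effective n 15 do not fit: a single visit gives 1.02 at every r, a change score 1.29 falling to .65, and baseline-adjusted analysis 1.00 falling to .61.

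**Step 3: what the product does to clinic variance.** Multiplying (1+r)/2 by 1.744 makes the clinic component .093 × (1+r)/2. At r = .20 this is .093 × .60 = .056. Under a constant clinic intercept it stays at .093.

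**Step 4: hold clinic variance constant.** The variance of an arm mean is {[(1+r)/2 − ICC]/9 + ICC}/3.
- r = .20: [(.60 − .093)/9 + .093]/3 = .1493/3 = .0498; SE of the difference = √(2 × .0498) = .316
- r = .80: [(.90 − .093)/9 + .093]/3 = .1827/3 = .0609; SE of the difference = √(2 × .0609) = .349

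Equivalently, the ICC of the two-visit mean is .093/.60 = .155 at r = .20 and .093/.90 = .103 at r = .80, with design effects 1 + 8(.155) = 2.24 and 1 + 8(.103) = 1.83.

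| r | Printed method (n = 15, normal) | Corrected, normal | Corrected, 52 df | Power at the printed-method figure (normal; 52 df) |
|---|---|---|---|---|
| .20 | .79 | .88 | .90 | 71%; 69% |
| .50 | .89 | .93 | .95 | 76%; 75% |
| .80 | .97 | .98 | 1.00 | 79%; 78% |

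The plan prints only the two ends; the middle row is computed by the same method.

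**Step 5: sensitivity.** If r is read as the correlation within clinic, the 52-df range is .91 to 1.00. With the same variance and 4 df (six clinics minus two arms), the range is 1.19 to 1.31.

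**The case against.** **The formula is inferred.** The plan does not print it, and a second route, 4 df with no ICC, gives .793 and .971, which also round to the printed range. That route contradicts the plan's statement that an ICC of 9.3% was assumed. The interval width of 27.9% and the distance of .30 both need an effective sample of 46. The design-effect route is therefore much the better supported, though still an inference.

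**The ICC may not be a single-visit quantity.** The plan calls it "a clinic-based conservative unconditional ICC of 9.3" percent and does not say whether it is the clinic share of one visit's score or of the score analysed. If it were the share for the two-visit mean, 1.744 would be the right design effect and the printed range would stand. This objection holds as a condition on the result. A single ICC is quoted for every calculation, including those with no repeated measure, so the single-visit reading is the natural one, but the plan should say so.

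**A treatment-by-time contrast would cancel a constant clinic intercept.** That is correct, but the printed figures rise with r, and a change contrast would fall with r.

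**Little depends on the range.** The plan plays down significance testing, offers the power figures as supplementary, and does not derive its 9 clinics and 90 dyads from them. This stands, and it limits the importance of the point.

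**Stronger readings that the documents do not support.** A reader might infer that the whole range is overstated by about 11 points of power; that shortfall belongs to r = .20 only. A reader might also take .79 as a claim that effects just under .80 are detectable. The plan makes no such claim: .79 is only the lower end of a range, and the summary speaks of large effects.

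**Conclusion.** The point holds. Under the planned clinic intercept, the printed differences do not have the stated 80% power. At r = .20 the detectable difference is about .88 to .90 rather than .79, and power for .79 is about 69% to 71%. At r = .80 it is about .98 to 1.00 rather than .97, and power for .97 is 78% to 79%. The error therefore matters mainly at low r, and the plan's label of large effects survives.

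The result assumes that 9.3% is the single-visit clinic share, 9 children per clinic, two-sided alpha, equal variance at the two visits, and a time-averaged contrast.

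It would be a mistake to read .90 to 1.00 as the true detectable range of this design. That range isolates one correction and keeps child-level df, whereas each comparison rests on six randomised clinics. The choice of df moves the answer more than this correction does.

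**What to change.** In the Power Analyses paragraph of C.3.6 Data Analysis:

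1. Recompute the range with arm-mean variance {[(1+r)/2 − ICC]/9 + ICC}/3.
2. State that the 9.3% ICC is the clinic share of variance at a single visit. If it is not, say what it is and why 1.744 applies.
3. State the contrast and the reference distribution. If .90 to 1.00 is printed, say that it uses child-level df, and give the figure on 4 clinic-level df, about 1.19 to 1.31, beside it.
4. Bring the summary sentence into line with the recomputed range. The word large can stay.

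The cost is one recalculation and a few sentences. Enrolment and conduct are unaffected. The downside is a less favourable stated detectable difference.
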